#### 8.4 Treatment Compliance

Treatment compliance on administration volume (1.0 mL or any other amount) of investigational drug will be measured.

#### 8.5 Efficacy Analyses

Efficacy analyses will be performed for the ITT population.

The following efficacy endpoints will be analyzed using the appropriate parametric or nonparametric statistical method:

- Worst leg pain during the past 24 hours assessed by VAS from baseline through Week 26
- Worst back pain during the past 24 hours assessed by VAS from baseline through Week 26
- Functional disability measured by the ODI from baseline through Week 26
- Change of neurological status from baseline determined by neurological examinations FNS or SLR test, sensation, muscle strength, and deep tendon reflex) from baseline through Week 26
- Occurrence of post-treatment surgery for lumbar disc herniation at the same level of administration of the investigational drug up to Week 26

The descriptive statistics of the worst leg pain, back pain, ODI, and their change from baseline will be calculated and presented for each time point. A longitudinal plot will be used to display the mean change from baseline and the associated 95% confidence intervals (CIs) at each time point.

For analysis of change of neurological status from baseline, the number (%) of patients with negative FNS or SLR test results, negative neurological tests for hypoesthesia, muscle weakness, or diminished deep tendon reflex results will be presented for each time point. Furthermore, the percentage of patients with a negative neurological test will be calculated and presented for each time point. The time-course changes will also be presented graphically with bar chart by time points.

In the analysis of occurrence of post-treatment surgery for lumber disc herniation at the same level of administered disc, the number (%) of patients having such surgery will be calculated and presented.

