#### 3.2.2 Secondary Efficacy Endpoints

The following secondary efficacy endpoints will be assessed at the times specified in the schedule of events and overall time-course, and changes from baseline will be analyzed:

- Worst leg pain during the past 24 hours assessed by VAS.
- Worst back pain during the past 24 hours assessed by VAS.
- Functional disability measured by the Oswestry Disability Index (ODI).
- Change of neurological status from baseline determined by neurological examinations:
  - Femoral Nerve Stretching (FNS) test for patients with lumbar disc herniation L1–L2, L2–L3, or L3–L4 or
  - Straight Leg Raising (SLR) test [for patients with lumbar disc herniation L4–L5 or L5–S1, and
  - Sensation, muscle strength, and deep tendon reflex.
- Occurrence of post-treatment surgery for lumbar disc herniation at the same level of administration of the investigational drug up to Week 26 including patients who discontinued from the study.

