#### 6.1.7 Neurological Examinations and Pain Assessments

Neurological examinations and pain assessments will be performed in accordance with the schedule of assessments Table 3.

Neurological testing will include an FNS or SLR test, sensation, muscle strength, and deep tendon reflex. Any neurological finding that worsens after the administration of the investigational drug and that is considered to be clinically significant in the Investigator's judgment meets AE reporting criteria.

Cases where leg pain or back pain increase over the Screening period (baseline value) and, in the Investigator's judgment, is clinically aggravated, meet AE reporting criteria. Cases considered clinically exacerbated, in the Investigator's judgment, based on post treatment improvement followed by the reappearance of pain of equal severity than before improvement meet AE reporting criteria.

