#### 8.2 General Considerations

Categorical variables will be summarized in a contingency table by the number and percentage of patients in each category. Continuous variables will be summarized by the number of observations, mean, standard deviation (SD), median, inter-quartile range, minimum, and maximum. Where data are collected over time, both the observed data and change from the Screening period (baseline) will be summarized at each time point. All eCRFs collected and derived data will be listed.

Methods for imputation of missing data and criteria for inclusion of patients in efficacy analyses will be specified.

All statistical tests will be performed 2-sided with a significance level of 5%, unless otherwise stated.

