# 8.8 Determination of Sample Size

The total number of 1000 patients will be enrolled. In order to further characterize the frequency and outcome of the rather infrequent treatment-related AE, the current study will have approximately 1000 patients treated with SI-6603. This sample size will allow for estimating a cumulative incidence rate of 0.3% (n=3 patients with events) with a 95% CI of (0.06%, 0.87%), or an incidence rate of 1.5% (n=15 patients with events) with a 95% CI of (0.84%, 2.46%). This calculation assumes that distribution of treatment-related AE is binomially distributed. The 95% CI is calculated using the Clopper-Pearson method in SAS 9.2.

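### Section 8.5 reduces neurological change from baseline to the percentage negative at each visit, so new sensory, strength and reflex deficits offset recoveries in the planned tables, and only worsening judged clinically significant is counted, as adverse events

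*Combined protocol and SAP*

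**What the plan says.** Section 3.2.2 lists among the secondary efficacy endpoints "Change of neurological status from baseline determined by neurological examinations". The components are the femoral nerve stretching (FNS) or straight leg raising (SLR) test, sensation, muscle strength and deep tendon reflex.

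For this endpoint Section 8.5 names three outputs:
- the number and percentage of patients with a negative FNS or SLR test, together with "negative neurological tests for hypoesthesia, muscle weakness, or diminished deep tendon reflex results will be presented for each time point";
- a percentage, described as follows: "Furthermore, the percentage of patients with a negative neurological test will be calculated and presented for each time point";
- a chart: "The time-course changes will also be presented graphically with bar chart by time points".

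None of these links a patient's result at a visit to the same patient's baseline result, and none carries a confidence interval. In the same section, leg pain, back pain and ODI do get change from baseline.

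The neurological examination also appears under safety variables. Section 6.1.7 makes it an adverse event matter in these terms: "Any neurological finding that worsens after the administration of the investigational drug and that is considered to be clinically significant", with the investigator as judge. Section 8.6.1 then reports adverse event incidence with 95% CIs by system organ class, preferred term and severity. Sections 8.6.1 to 8.6.10 contain no analysis of the neurological examination itself. By contrast, Sections 8.6.8 and 8.6.9 specify shift tables against baseline for Modic and Pfirrmann results, plus the percentage changed or worsened with a 95% CI.

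**The concern.** The endpoint is a within-patient change, and the stated method is a marginal percentage. A patient with normal strength at baseline who becomes weak lowers the percentage negative by exactly as much as a recovering patient raises it. If recoveries outnumber new deficits, the chart shows improvement whatever the number of new deficits behind it.

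This matters because the primary objective is safety. Section 1.1 presents the drug as carrying less risk of nerve tissue injury than chymopapain, and Section 9.10 lists significant neurologic deficit among the events that may warrant stopping the study. A reader of the report will want two numbers for each component: how many patients with a deficit at baseline recovered, and how many without one acquired one. Section 8.5 as written produces neither for sensation, strength or reflex.

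**Working it through.** **Inputs from the documents.** Section 8.8 gives the size: "the current study will have approximately 1000 patients treated with SI-6603". It also gives the interval method: "The 95% CI is calculated using the Clopper-Pearson method in SAS 9.2". The documents give no baseline, new-deficit or recovery rates for sensation, strength or reflex, so those below are assumptions.

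**The plan's own figures.** Exact Clopper-Pearson limits give 0.062% to 0.874% for 3/1000 and 0.842% to 2.462% for 15/1000. Both agree with the intervals printed in Section 8.8. The point does not dispute any stated figure.

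**Identity.** For one component with complete data, let B be the number negative at baseline, d the number newly positive at the visit and r the number who recovered. Then

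negative at visit = B − d + r.

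The tables in Section 8.5 show B and B − d + r, so they reveal only r − d.

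**Illustration.** Assume N = 1000, B = 600 (so 400 abnormal at baseline) and a net gain of r − d = 100. New-deficit rates are d/600 with exact 95% CIs; recovery rates are r/400.

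| New deficits d | Recoveries r | Section 8.5 shows | New deficit among those normal at baseline | Recovery among those abnormal at baseline |
|---|---|---|---|---|
| 0 | 100 | 70.0% negative | 0% (0 to 0.61%) | 25.0% |
| 20 | 120 | 70.0% negative | 3.33% (2.05 to 5.10%) | 30.0% |
| 50 | 150 | 70.0% negative | 8.33% (6.25 to 10.84%) | 37.5% |
| 100 | 200 | 70.0% negative | 16.67% (13.77 to 19.89%) | 50.0% |

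Check of the last row: 600 − 100 + 200 = 700, and 700/1000 = 70.0%.

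**Sensitivity to the baseline assumption.** Hold d = 50 and r = 150. The new-deficit rate is 10.0% (7.51 to 12.97%) for B = 500, 7.14% (5.35 to 9.31%) for B = 700 and 6.25% (4.67 to 8.16%) for B = 800. In each case the Section 8.5 output shows only a 10-point gain.

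**Which components are affected.** Inclusion criterion 3 (Section 4.1) requires a positive FNS or SLR test on the symptomatic side. For that test B = 0 among eligible patients, so d = 0 and the percentage negative is already the recovery rate, apart from missing data. Offsetting concerns sensation, muscle strength and deep tendon reflex.

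**The case against.** A reader might infer that new deficits after injection cannot be seen anywhere in this study. The documents do not support that.
- Worsening judged clinically significant is an adverse event under Section 6.1.7 and is reported with incidence and 95% CI under Section 8.6.1.
- Section 4.3.1 treats withdrawal for a significant neurologic deficit as withdrawal for an adverse event, and Section 7.2.7 repeats the neurological examination at discontinuation.
- Section 8.2 requires all collected data to be listed.
- Table 1 shows that hypoaesthesia (8/269, 3.0%) and muscular weakness (1/269, 0.4%) were reported as adverse events on SI-6603 in earlier studies.

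This stands, and it narrows the gap to changes not judged clinically significant, to incidence among patients normal at baseline, and to recovery. Adverse event tables supply none of these, and a listing for about 1000 patients is not a planned estimate.

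A reader might also infer a very large hidden number. If 60% negative rose to 78%, the net gain would be 180 and at most 400 could recover, so up to 400 − 180 = 220 new deficits would be arithmetically possible. That is a ceiling on assumed rates: every abnormal patient would have to recover and 220/600 = 36.7% of normal patients would have to acquire a deficit. Nothing in the documents suggests such a rate.

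Finally, Section 8.2 has a general rule to summarise categorical variables in contingency tables and to summarise change from baseline at each time point, and Section 8 leaves detailed methods to a SAP finalised before database lock. So a within-patient table is not excluded. But the general rule gives no form for a binary result, while Section 8.5 does give a specific method for this endpoint, and that method is marginal.

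**Conclusion.** The point holds for sensation, muscle strength and deep tendon reflex. Section 8.5 presents a cross-sectional percentage as its analysis of change from baseline, so new deficits and recoveries offset each other in the planned tables, and Section 8.6 does not fill the gap. The identity needs only complete data. The illustrated sizes (0% to 16.7% new deficits behind the same 70.0%) rest on assumed rates and show what the tables cannot distinguish, not what is expected.

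This is a reporting weakness in a secondary endpoint that bears on safety. It leaves the primary adverse event analysis intact and should be corrected while the SAP is still open. Section 8.5 also does not say how the discontinuation examination enters the per-visit tables. It would go too far to conclude that withdrawn patients are lost from the denominators, because no per-visit denominator is stated and Section 8.2 leaves imputation to be specified.

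**What to change.** In Section 8.5, cross-referenced in Section 8.6 for the safety population, add baseline-by-visit shift tables for sensation, muscle strength and deep tendon reflex. The ITT and safety sets are defined identically in Section 8.1.2, so one set of tables serves both. For each of the three components report, with exact 95% CIs:
- (a) the percentage of patients abnormal at baseline who become normal;
- (b) the percentage of patients normal at baseline with a new deficit at any post-baseline visit, including the discontinuation visit.

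For FNS or SLR report (a) only, since eligible patients are positive at entry. Keep the existing percentages and bar chart.

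The cost is SAP wording and a few more tables. The examinations are already scheduled in Table 3 at Screening, Weeks 1, 6, 13 and 26, and discontinuation. The downside is that (b) will include some transient or examiner-variable findings, across many sites and with no comparator arm. It should therefore be presented beside the adverse event incidence, with a note on that limitation.

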#### 8.6 Safety Analyses

Evaluation of the safety of SI-6603 will be based on the occurrence of AEs, vital signs, laboratory, imaging, and other clinical assessments. The safety analyses will use the safety population.

# 8.6.1 Adverse Events and Treatment-Related Adverse Events

The incidence of AEs and associated 95% CIs will be determined and presented. A similar analysis will be conducted for each level of severity. After the terms of AEs observed are coded with corresponding MedDRA terms, data on the incidence of AEs will be compiled for each system organ class (SOC) or preferred term (PT). Furthermore, data on the incidence of AEs, as classified by SOC or PT, will be compiled for each level of severity. Of the AEs observed, those whose causal relationship to the investigational drug is classified as "related" will be defined as treatment-related AEs and evaluated in the same manner as AEs.

Concerning SAEs, their incidence and associated 95% CIs will be determined and presented. In addition, data on the incidence of SAEs, as classified by SOC or PT, will be compiled. The same analyses will be repeated for SAEs classified as "related".

# 8.6.2 Vital Signs

For body temperature, blood pressure, heart rate and respiration rate, descriptive statistics will be calculated at each time point.

#### 8.6.3 Laboratory Tests

For laboratory data, descriptive statistics will be calculated for each time point.

# 8.6.4 Serum Anti-SI-6603 Antibody

The proportion and 95% CI of patient with serum anti-SI-6603 antibody positive will be calculated for each group at each time point. Furthermore, the proportion of each isotype of immunoglobulin (IgG, IgM and IgE) will be calculated. The proportion and 95% CI of patient with immunogenicity status will be calculated for each group at each time point.

# 8.6.5 Disc Height (Disc Index)

For the change from baseline and percent change from baseline of intervertebral disc height, descriptive statistics will be calculated at each time point to make a time-course change plot. The percentage of the patients who showed an intervertebral disc height change of  $\leq$ 30% and associated 95% CIs will be calculated and presented.

Association between decreased intervertebral disc height and leg pain (VAS) or back pain (VAS) will be assessed.

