# 1.1.2.6 Phase II Clinical Study in Patients with Lumbar Disc Herniation (Study Number: 6603/1121) (USA)

This study was an open-label, multicenter, sequential dose-escalation study. The objective of this study was to evaluate the safety of SI-6603 in lumbar disc herniation patients (L4–L5 or L5–S1) followed for 52 weeks after administration of SI-6603 into an intervertebral disc. Exploratory efficacy endpoints were investigated. Patients received a single 1.0 mL injection of SI-6603 (0.5 U, 1.25 U, or 2.0 U) into the nucleus pulposus of an intervertebral disc of each patient. A Data Safety Monitoring Board (DSMB) evaluated safety and tolerability once the Week 13 data were available for each cohort. On the basis of the recommendation of the DSMB, the Sponsor proceeded to the next higher dose for the second (1.25 U) and third cohorts (2.0 U).

A total of 17 patients (94.4%) in the safety population experienced 39 AEs. Two patients (11.1%) discontinued the study due to an AE and no patient discontinued due to a treatment-related AE. No patient experienced a SAE or died during the study.

The most frequently observed treatment-related AE with an incidence of  $\geq$ 3 patients in the total safety population was nuclear MRI abnormal (4 patients, 22.2%). The event was all mild in intensity and did not require intervention in all patients. The following 3 treatment-related AEs (each reported for a different patient) were not resolved before the end of the study: nuclear MRI abnormal, spinal X-ray abnormal, and dysesthesia.

Seikagaku Corporation	Clinical Study Protocol
Protocol Number 6603/1132	CONFIDENTIAL

Clinical observations of the patients with these treatment-related AEs were terminated after each patient's condition was determined to be stable.

Evaluation of translation and angulation of vertebral bodies did not raise safety concerns. One patient had a decrease in disc height  $\geq$ 30%. Overall, 6 patients (33.3%) in the safety population had a change to Modic classification Type I or II, which included 1 patient (20.0%) in the 0.5 U dose group, 3 patients (50.0%) in the 1.25 U dose group, and 2 patients (33.3%) in the 2.0 U dose group.

No patient had an increase in serum anti-SI-6603 IgE antibody titer. At Week 13, one patient each from the 0.5 U, 1.25 U and 2.0 U dose groups had an IgG antibody titer that was increased by one grade from baseline, but with unclear SI-6603 specificity.

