#### 1.3.1.4 Decrease of Lumbar Disc Height and Change in Bone Marrow Adjacent to Vertebral Endplates

In past studies with SI-6603 administration, treatment-related AEs of nuclear MRI abnormal (change in bone marrow adjacent to vertebral endplates; Modic change) were reported in 22.3% (60/269 patients) and spinal X-ray abnormal were reported in 14.1% (38/269 patients). Among 38 patients reporting spinal X-ray abnormal, AEs included intervertebral posterior angle dilation (7 events) and 30 % decrease of disc height (34 events). However, none of the affected patients exhibited any clinical symptoms posing safety concerns. Furthermore, there was no leg pain or back pain accompanying the occurrence of instability of the intervertebral disc and surrounding tissues. The clinical significance of Modic changes remains unclear and past SI-6603 studies did not reveal any increase of leg pain or back pain in conjunction with Modic changes.

Spinal imaging changes following lumbar discectomy were reported by McGirt, et al. as 18%, 21%, and 26% decreases of disc height at 3 months, 6 months, and 2 years post surgery, respectively. In a follow-up study until 2 years after lumbar discectomy patients, Ohtori, et al. reported Modic changes in 7 (15.6%) of the 45 patients, with 1 of the 22 patients exhibiting a change from Modic Type 0 to Type 1, 3 of the 22 patients changing from Modic Type 0 to Type 2, and 3 of the 23 patients changing from Modic Type 0 to Type 2, and 3 of the 23 patients changing from Modic Type 1 to Type 2. In a Phase II/III study in Japan, percent decrease in disc heights was highest in the 5 U dose group at 17.4% at Week 13, 18.9% at Week 26, and 21.8% at Week 52. The reductions in disc height in the SI-6603 groups were equal to or milder than those of the above-mentioned lumbar discectomy patients. The incidence of treatment-related Modic changes was slightly higher in the SI-6603 groups than in the lumbar discectomy patients at 22.3%.

There is a possibility that changes in the bone marrow adjacent to vertebral endplates and decreases of lumbar disc height may occur as the result of SI-6603 administration in the

Seikagaku Corporation	Clinical Study Protocol
Protocol Number 6603/1132	CONFIDENTIAL

same degree as seen in lumbar discectomy. In addition, there is a possibility of vertebral body instability (intervertebral posterior angle and vertebral body translation).

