#### 6.1.1.2 Definitions

An AE is any untoward medical occurrence that occurs in a patient or clinical investigation subject administered a pharmaceutical product, and which does not necessarily have a causal relationship with this treatment. An AE can therefore be any unfavorable and unintended sign (including abnormal laboratory finding), symptom, or disease temporally associated with the use of an investigational product, whether or not considered related to the product.

For this study, the following imaging findings will be recorded as AEs:

- Disc height (disc index): decrease in disc height ≥30% compared to baseline value
- Vertebral posterior angle: vertebral body angle formed by flexion of  $\geq 5^{\circ}$
- Vertebral body translation: vertebral body translation of  $\geq 3 \text{ mm}$
- Change in vertebral body endplates and adjacent bone marrow: Type 1, Type 2, or Type 3 change (Modic Classification)

Note: The above events are limited to the targeted level of the procedure and the adjacent vertebral bodies.

All AEs, including intercurrent illnesses, occurring during the study will be documented in the eCRF. Concomitant illnesses, which existed before entry into the study, will not be considered AEs unless they worsen during the treatment period. All AEs, regardless of the source of identification (e.g., physical examination, laboratory assessment, or reported by patient), must be documented.

Pre-existing conditions will be recorded in the eCRF on the Medical History or appropriate page.

A treatment-emergent adverse event will be defined as an AE that begins or that worsens in severity after the study drug has been administered.

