# 6.1.3 X-ray Imaging

Disc height, intervertebral posterior angle, and translation of vertebral body will be assessed by X-ray in accordance with the schedule of assessments Table 3.

The following will be reported as AEs:

- a decrease in disc height  $\geq 30\%$  compared to baseline
- vertebral body angle formed by flexion of  $\geq 5^{\circ}$
- vertebral body translation of  $\geq 3 \text{ mm}$

Events are limited to the targeted level of the investigational drug administration and the adjacent vertebral bodies (see Appendix 11.7).

Anteroposterior and lateral-intermediate, flexion, and extension spinal x-rays will be obtained according to the "*Procedure Manual for Radiographic Examinations of the Lumbar Spine*". The X-ray images obtained will be sent to the central imaging reader (BioClinica) for assessment.

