#### 6.1.3.1 Disc Height (Disc Index)

The central imaging reader will measure the disc index for the intervertebral disc treated with the investigational drug using

- a) the posterior height of the superior vertebral body adjacent to the target segment,
- b) the anterior disc space, and
- c) the posterior disc space.

A decrease in disc height  $\geq$ 30% compared to baseline value will be recorded as an AE (see Appendix 11.7 for additional details regarding imaging tests).

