# 8 STATISTICAL METHODS

The statistical considerations summarized in this section outline the plan for data analysis of this study.

Before database lock, a Statistical Analysis Plan (SAP) will be finalized, providing detailed methods for the analyses outlined below. The analyses specified in the SAP will be performed and the Clinical Study Report (CSR) will be prepared upon database lock. Any changes from the planned analyses will be described and justified in the final CSR.

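### Section 8.6.5 tabulates a disc-height change of ≤30%, but the defined adverse event is a decrease of ≥30%, so the rule as written does not count the event

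*Combined protocol and SAP*

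**What the plan says.** Section 8.6.5 first asks for descriptive statistics and a time-course plot of change and percent change in disc height. It then says that the percentage of patients with an "intervertebral disc height change of $\leq$ 30% and associated 95% CIs will be calculated and presented". The rule has no minus sign and does not say that the change is a loss. The section states no sign convention.

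The event is defined in three other places:

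- Section 6.1.1.2 lists, among imaging findings to be recorded as AEs, "Disc height (disc index): decrease in disc height ≥30% compared to baseline value".
- Section 6.1.3 lists "a decrease in disc height" of ≥30% from baseline among the X-ray findings to be reported as AEs.
- Section 6.1.3.1 says that a ≥30% decrease "compared to baseline value will be recorded as an AE".

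The next paragraph of 8.6.5 shows the intended direction: "Association between decreased intervertebral disc height and leg pain (VAS) or back pain (VAS) will be assessed".

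**The concern.** The threshold in the analysis section points the opposite way from the threshold in the definitions. A programmer who follows 8.6.5 literally would produce a table of patients who did not have the event, or of almost all patients, under a heading that readers would take as the rate of disc-height loss.

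This matters because safety is the primary objective (Section 2.1) and change in disc height is a listed safety endpoint (Section 3.2.1). Section 1.3 names loss of disc height among the more common possible risks. Section 8.6.5 is also the only place that promises a percentage with a 95% confidence interval for this finding alone.

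**Working it through.** **1. Direction of each imaging rule.**

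| Finding | AE definition (6.1.1.2, 6.1.3) | Analysis rule | Same direction? |
|---|---|---|---|
| Disc height | decrease ≥30% | change ≤30% (8.6.5) | No |
| Posterior angle | ≥5° | ≥5° (8.6.6) | Yes |
| Translation | ≥3 mm | ≥3 mm (8.6.7) | Yes |

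Only the disc-height rule is reversed.

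**2. What the rule counts.** Let D be the percent change from baseline, with a loss negative. The defined event is D ≤ −30.

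- *Size of change:* |D| ≤ 30. Apart from values of exactly 30%, and if gains above 30% do not occur, this is the complement of the event.
- *Signed change:* D ≤ +30. This takes in every loss of any size and every gain up to 30%.
- *With a minus sign restored:* D ≤ −30. This is the event.

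**3. Interval method.** Section 8.8 names the Clopper-Pearson method for its own intervals at n = 1000. For x events in n, the lower limit is the 0.025 quantile of Beta(x, n − x + 1) and the upper limit is the 0.975 quantile of Beta(x + 1, n − x). The plan's figures reproduce: 3/1000 gives 0.06% to 0.87%, and 15/1000 gives 0.84% to 2.46%. They are not affected by this point.

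**4. Illustration at n = 1000, all patients evaluable.** The documents give no 26-week disc-height rate at 1.25 U, so 5% to 20% is an assumption.

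| Assumed event rate | Intended output (95% CI) | Size-of-change reading (95% CI) |
|---|---|---|
| 5% | 50/1000 = 5.0% (3.73 to 6.54) | 950/1000 = 95.0% (93.46 to 96.27) |
| 20% | 200/1000 = 20.0% (17.56 to 22.62) | 800/1000 = 80.0% (77.38 to 82.44) |

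On the signed reading the output is close to 1000/1000 = 100% (99.63 to 100). As a check, assume normally distributed changes with a mean loss of 10% to 21.8% and an SD of 10 to 20 percentage points. The share with D ≤ +30 is then 97.7% to 100%. The 21.8% is the Week 52 mean loss at 5 U in Section 1.3.1.4; the other values are assumptions.

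**5. Nearest figures in the documents.** None is at both the study dose and the study duration.

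- US Phase II study (Section 1.1.2.6; 0.5 to 2.0 U, 52 weeks): "One patient had a decrease in disc height" of ≥30%. The safety population is 17/0.944 = 18, so the rate is 1/18 = 5.6%.
- Pooled studies (Section 1.3.1.4): 34 treatment-related events among 269 patients at mixed doses, so at most 34/269 = 12.6%. At n = 1000 that would be 126 patients, 12.6% (10.6 to 14.8). The size-of-change reading would report 874, 87.4% (85.2 to 89.4).
- Japanese Phase III study at 1.25 U (Section 1.1.2.7, followed to 52 weeks): 23.2% with treatment-related spinal X-ray abnormal, a term not confined to disc height. At n = 1000, 232 patients, 23.2% (20.6 to 25.9), against 768, 76.8% (74.1 to 79.4), on the size-of-change reading.

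**The case against.** The strongest reply is that this is one missing character. Percent change is normally a signed variable, ≤ −30% is the natural way to write a decrease of ≥30%, and three sections fix the definition. A careful programmer would see the intent. That is fair, and it is why the correction is easy. It does not make the printed rule right.

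The minus sign may have been lost when the PDF was read. This cannot be excluded, and the source should be checked. However, the minus in the −5° threshold of Section 6.1.3.2 survived, and the 8.6.5 rule also lacks any word for a decrease.

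The listed endpoint is change in disc height, which the first sentence of 8.6.5 analyses properly. Events of ≥30% loss must also be recorded as AEs, summarized under Section 8.6.1 and listed under Section 8.2. This stands: the information is not lost, and the descriptive statistics would probably reveal the error. The AE tables may still not replace the dedicated rate. Section 8.6.1 compiles by system organ class or preferred term, and in past studies spinal X-ray abnormal covered both findings: "AEs included intervertebral posterior angle dilation (7 events) and 30 % decrease of disc height (34 events"). How this study will code them is not stated.

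Finally, Section 8 says "Before database lock, a Statistical Analysis Plan (SAP) will be finalized", with detailed methods for the analyses outlined there. That gives an opportunity to correct the rule, but the outline should not send the SAP in the wrong direction.

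**Conclusion.** The concern holds. As printed, the percentage in Section 8.6.5 contradicts the AE definition in three sections, and no sign convention in the document reconciles them. Programmed literally, the table would report the complement of the event rate (95% to 80% for assumed true rates of 5% to 20%) or about 100%. Those figures are illustrative and rest on the assumed rates and on all 1000 patients being evaluable. The direction of the threshold does not depend on them. The point should be fixed, but it does not threaten the study: the intent can be inferred and the underlying events are captured elsewhere. The one reservation is that the source PDF should be checked for a lost minus sign.

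**What to change.** In Section 8.6.5, replace the condition with a decrease from baseline of ≥30% (percent change ≤ −30%), as in Sections 6.1.1.2, 6.1.3 and 6.1.3.1. State that a loss of height is a negative change, and carry the same condition into the SAP before database lock.

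In the same edit, one sentence could clear up a smaller ambiguity about the angle, which carries no weight in the conclusion. Section 6.1.3.2 enters the posterior angulation label in the eCRF at ≤ −5° but records the AE at ≥5°, and 8.6.6 uses ≥5°. The measurement figure is not shown, so this may be only an unstated sign convention. Stating the convention once would reconcile these sentences.

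The cost is a one-line correction and one clarifying sentence. No new data, visits or image readings are needed.
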